## 6b Any changes to trial outcomes after the trial commenced

NONE

## 7a Sample size

The total number of contact/treatment days in the centre (out-patient clinic, inpatient ward and emergency team) in 2021 was 14.621 = 1250 contact days per 100 patients.

Based on a standard deviation of 100 days, Type 1 error level of 5%, a 5% expected reduction of total number of contact days per year in the intervention group, we will need 64 patients in the intervention group and 64 patients in the control group in order to obtain a statistical power of 0,80.

Currently around 300 patients are on waiting list. Prioritizing long waiting time we enroll and randomize 256 patients in the trial:

- 64 patients in trial group A (3-day course) & 64 patients in control group A.
- 64 patients in trial group B (1-day course) & 64 patients in control group B.

So we expect this to be a reliable study with acceptable statistical power.

---

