### 4a Participants

All norwegian speaking patients on the outpatient clinic waiting list are considered eligible for the study. Thus no patients will be a priori excluded from the study population for any clinical reason - for instance diagnosis, co-morbidity, symptom severity or use of medicine or other kinds of treatment.

So this is an intention-to-treat & naturalistic/pragmatic trial design.

No patients will be excluded from *treatment as usual* because of the trial.

---

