## 6a Outcomes

Primary outcome will be *use of mental health hospital services* measured by the number of contact/treatment days to the centre (in-patient, out-patient and emergency team contacts) in a 12 month follow up period from the day of intervention start. This outcome measure is considered to have a high face validity and to be a reliable proxy measure for patient wellbeing when applied within a consistent organizational context (Burns 2007, Addington 2012).

Secondary outcomes will be:

- Average change in score *before and 6 months after* intervention on a 3 item anonymous mental wellbeing questionnaire - see Appendix 1.
- Medication level based on pharmacy data.

The use of standard patient record data as outcome measures is in line with the Recommendation on Criteria for Establishing Strong Evidence of Effectiveness from a National Academies Report (O'Connell 2009).

A trial group sample of participants will be interviewed for a qualitative research study.

---

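### The sample size is planned from a centre-wide 2021 contact rate, while the trial enrols outpatient waiting-list patients, and nothing in the protocol shows that the rate carries over

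*Protocol*

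**What the plan says.** Section 7a takes its base from the centre as a whole: "The total number of contact/treatment days in the centre", over the three services, with the total and rate given as "out-patient clinic, inpatient ward and emergency team) in 2021 was 14.621 = 1250 contact days per 100 patients". The other inputs are "Based on a standard deviation of 100 days", "Type 1 error level of 5"% (one- or two-sided is not stated), an expected 5% fall in yearly contact days in the intervention group, and power 0.80. The result is 64 patients per group, used once for delivery model A and once for B.

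The patients come from a narrower source. Section 4a states: "All norwegian speaking patients on the outpatient clinic waiting list are considered eligible for the study". Section 7a puts the list at around 300 and adds: "Prioritizing long waiting time we enroll and randomize 256 patients in the trial". Under section 5 they keep their place on the list and retain access to assessment and usual treatment.

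The primary outcome in 6a is the "number of contact/treatment days to the centre (in-patient, out-patient and emergency team contacts) in a 12 month follow up period", with the clock running from each patient's intervention start.

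**The concern.** The services counted in the planning base and in the outcome are the same; the patients and the time window are not. The base is a calendar-year total over everyone who appears in its denominator. The outcome is a forward 12-month count, from a personal start date, for people waiting for outpatient care and chosen for long waits. Their rate could be lower, because part of the window may be spent waiting and the centre total includes ward days. It could be higher, because a first treatment year may be intensive. The protocol offers nothing to settle this.

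Because the effect is a percentage, the base decides how many days the trial sets out to detect. The 0.80 power in 7a, and that section's statement that power is acceptable, depend on that number and on the SD beside it. Correcting the arithmetic while keeping 1250 per 100 would still describe other patients.

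**Working it through.** **Inputs (Protocol 7a):** 14,621 days; 1250 days per 100 patients; SD 100 days; type 1 error 5%; 5% reduction; power 0.80; 64 per group. Allocation is 1:1 (3a).

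**Implied denominator.** 1250/100 = 12.5 days per patient, and 14,621/12.5 = 1,169.7, so about 1,170 patients. The waiting list holds around 300. That the 1,170 are all patients treated in 2021 is an inference; the protocol does not define the denominator.

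**The target in days.** 5% × 1250 = 62.5 days per 100 patients, or 0.625 day per patient.

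**Reproducing 64.** For two means, two-sided 5% and 80% power, n per group = 2 × (1.960 + 0.842)² × (SD/difference)² = 15.70 × (SD/difference)².

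- Both figures per 100 patients: 15.70 × (100/62.5)² = 40.2, so 41 (32 if one-sided).
- Both figures per patient: 15.70 × (100/0.625)² = 401,863 (316,547 if one-sided).
- A difference of 50 with SD 100: 15.70 × 4 = 62.8, so 63, or 64 with the t-distribution.

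Only the last gives 64. A difference of 50 is 5% of 1000 or 4% of 1250, not 5% of 1250. The stated number therefore does not follow from the stated base.

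**How far the base matters.** The documents give no waiting-list mean, so the means below are assumptions. The SD is held at 100 per 100 patients, the only scale on which 64 is near the right order; two-sided 5%.

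| Assumed mean, days per patient-year | 5% in days per 100 patients | n per group for 0.80 | Power at 64 per group |
|---|---|---|---|
| 5 | 25 | 252 | 0.29 |
| 8 | 40 | 99 | 0.62 |
| 10 | 50 | 63 | 0.81 |
| 12.5 (protocol) | 62.5 | 41 | 0.94 |
| 15 | 75 | 28 | 0.99 |
| 20 | 100 | 16 | >0.99 |

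**The same question per patient.** Patients are randomised individually, so the per-patient SD is what counts. For a 5% reduction, n = 15.70 × (SD/mean)²/0.05², so n depends on the ratio of SD to mean.

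- The smallest standardised difference that 64 per group detects with 0.80 power is √(15.70/64) = 0.495. The SD could then be at most 0.05/0.495 = 0.10 of the mean, or 1.26 days at a mean of 12.5.
- With A and B pooled (128 per group): √(15.70/128) = 0.350, a ratio of 0.14, or 1.78 days.
- If the SD equals the mean (assumption): n = 15.70/0.05² ≈ 6,280 per group whatever the mean. Power is about 0.06 at 64 and 0.07 at 128 per group.
- If the SD is 100 days per patient: power is about 0.05 at either size, the type 1 error level.

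**The case against.** Several points against the concern stand. The 5% is stated for the intervention group and has no source, so a reader who inferred that the expected reduction itself was taken from another population would go too far; only its conversion into days was. The outcome counts the same three services as the base. Section 4a excludes no one on clinical grounds and 4b expects a mixed population, so a centre-wide rate is not an absurd proxy. The silence on waiting-list use cuts both ways.

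A reader might also infer that these patients have no contact days until their wait ends, and so that the base is too high. Section 5 does not support that: usual assessment and treatment stay open to them, and 6a counts ward and emergency contacts from the first day. Nor do the documents support a numerical factor of error, since any such figure would divide one assumed scenario by another pointing the opposite way.

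Finally, the arithmetic and SD problem is the larger one. If the SD is 100 days per patient, power stays near the type 1 error level for any plausible base. That is right, and it limits this point to an addition to that defect. It does not remove it: a sound recalculation needs a mean and an SD, and both must come from the patients enrolled.

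**Conclusion.** The mismatch is plain in the text: the rate is centre-wide, the enrolled patients come from the outpatient waiting list with long waiters first, and nothing links the two. Its direction and size cannot be determined from the protocol. On the per-100 scale, assumed means of 5 to 20 days move the power at 64 per group from 0.29 to above 0.99. This is an illustration of sensitivity, not an estimate.

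The consequence is that the stated 0.80 is unsupported on three counts: the base describes other patients, 64 does not follow from the stated inputs, and an SD of 100 days is not reconciled with a mean of 12.5. A reader might go on to infer bias in the treatment comparison, or a misleading yardstick for the control mean. Neither is supported: inference rests on a concurrent randomised control group, and no section uses 1250 per 100 to judge results. This should be corrected, but it does not invalidate the comparison.

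**What to change.** From DIPS ARENA, which the Data protection section already names as the data source, extract a past cohort selected as the trial selects: Norwegian-speaking outpatient waiting-list patients, longest waiting first, each with a start date comparable to intervention start. Count contact days over the following 12 months across the outpatient clinic, ward and emergency team.

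In 7a, replace 1250 per 100 and SD 100 with the per-patient mean and SD of that cohort. State the expected reduction as a percentage and in days per patient, say whether the test is one- or two-sided, and restate the power for 64 per group and for the pooled 128 per group. Enrolment stays at 256.

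The cost is one retrospective query and a rewritten paragraph. Nothing changes for patients. The downside is that the restated power will probably be far below 0.80: unless the SD is about a tenth of the mean, 64 per group does not reach 0.80 for a 5% reduction. The statements in 7a and section 12 that lean on adequate power would then need to be toned down.

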### 3a Trial Design

This is a randomized clinical trial in which individual waiting list patients are allocated 1:1 into intervention group and control group.

---

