### 4b Settings

The outpatient clinic is a part of a general District Psychiatric Centre in North Norway (Harstad). The clinic is serving a population of 31.300 citizens (mixed rural & small city population in 4 municipalities: Harstad, Lødingen, Sjølsund & Kvarfjord). The centre also has an inpatient ward and an emergency team.

The centre treats all categories of psychiatric disorders with a broad range of psychoterapeutic, medical and somatic assessments and measures.

Because this is a naturalistic/pragmatic study the patient population will be a mix with respect to socio-demographic and psychopathological parameters - and with respect to length of waiting period & previous treatment measures.

According to The World Bank & OECD Norway is one of the richest countries in the world with low social inequality.

Relevant data for the study are collected from the electronic patient record system and a separate research survey database.

---

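### The stated inputs do not give 64 patients per arm, and on a per-patient scale power for a 5% reduction is far below 0.80 unless the SD is about a tenth of the mean

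*Protocol*

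**What the plan says.** Section 7a (Sample size) gives the 2021 activity of the whole centre as 14,621 contact days, expressed as "1250 contact days per 100 patients". It continues "Based on a standard deviation of 100 days", with a 5% type 1 error, and states that for "a 5% expected reduction of total number of contact days per year in the intervention group, we will need 64 patients", with as many controls, to reach power 0.80. It does not say whether the SD is per patient or per 100 patients, where it comes from, or whether the test is one- or two-sided.

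The figure is then used twice, once for each delivery model: "Prioritizing long waiting time we enroll and randomize 256 patients in the trial", as 64 against 64 for the 3-day course (A) and 64 against 64 for the 1-day course (B). The section closes: "So we expect this to be a reliable study with acceptable statistical power".

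Three other sections matter here. Section 3a says that "individual waiting list patients are allocated 1:1 into intervention group and control group". Section 6a counts each patient's contact days "in a 12 month follow up period from the day of intervention start". Section 12 (Subgroup analyses) cites the power calculation as its reason for expecting to analyse A and B separately.

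**The concern.** The protocol supplies every number needed to repeat its calculation, and the repeat does not give 64. The likely reason is a mismatch of units: a difference expressed per 100 patients is set against an SD with no stated base, and the result is read as a number of individual patients. This is an inference, since 7a does not show its formula.

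This is the only power statement for the primary outcome. If it is wrong, readers are told that the trial can detect a 5% reduction when it may have little more than the type 1 error rate as its chance of doing so. A non-significant result could then be taken as evidence against a 5% reduction that the trial could hardly have seen. The separate analyses of A and B rest on the same figure.

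**Working it through.** **Inputs.** From 7a: 1250 contact days per 100 patients, SD 100 days, alpha 0.05, 5% reduction, power 0.80, 64 per arm. Section 12a names ANOVA, which for two groups is the two-sample t-test. The normal approximation is n per arm = 2(z₁₋α/₂ + z₁₋β)²/d² = 2(1.960 + 0.842)²/d² ≈ 15.70/d². The results below are t-test values, two-sided unless noted; the very large n come from the approximation.

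**1. Where 64 comes from.** With d = 0.50, 15.70/0.25 = 62.8, and the t-test gives 63.8, so 64 per arm with power 0.801. The figure therefore matches a standardised difference of 0.50.

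**2. The stated inputs at face value.** 5% × 1250 = 62.5 and d = 62.5/100 = 0.625. The approximation gives 15.70/0.3906 = 40.2; the t-test gives 41.2, so 42 per arm (one-sided 32.4, so 33). At 64 per arm, power would be 0.939. The 64 is not reproduced.

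**3. What would give about 64.** Each of these departs from the text:
- a 4% reduction (50/1250), a base of 1000 (50/100) or an SD of 125 (62.5/125), each giving d = 0.50;
- d = 0.625 with alpha 0.025 and power 0.90, giving 65 per arm;
- d = 0.625 with 41 per arm inflated for 35% dropout, which the protocol does not mention.

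**4. All inputs per patient.** The mean is 1250/100 = 12.5 days and the difference is 0.05 × 12.5 = 0.625 day. The SD must be the between-patient SD. The protocol leaves this open, so three readings are shown:
- 100 is already per patient;
- 100 is the SD of a total over 100 independent patients, so the per-patient SD is 100/√100 = 10;
- an assumed Poisson SD of √12.5 = 3.54, which allows no differences between patients beyond chance.

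| Per-patient SD | d = 0.625/SD | Power, 64 per arm | Power, 128 per arm (A and B pooled) | n per arm for 0.80 |
|---|---|---|---|---|
| 100 | 0.00625 | 0.050 | 0.050 | about 401,900 |
| 10 | 0.0625 | 0.064 | 0.079 | 4,019 |
| 3.54 | 0.177 | 0.168 | 0.291 | 503 |

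**5. A result that needs neither the mean nor the unit.** A 5% reduction gives d = 0.05 × mean/SD = 0.05/CV, where CV = SD/mean. Power 0.80 needs d = 0.499 at 64 per arm, so CV = 0.05/0.499 = 0.100. At 128 per arm it needs d = 0.352, so CV = 0.05/0.352 = 0.142. At a mean of 12.5 days, a CV of 0.100 is an SD of 1.25 days, about a third of the Poisson value (1.25/3.54 = 0.35). For assumed CVs of 0.25, 0.5 and 1.0, power is 0.202, 0.087 and 0.059 at 64 per arm, and 0.357, 0.125 and 0.068 at 128.

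**6. Sensitivity to the control mean.** The 12.5 days describe all centre patients, while the trial favours long waiters. For assumed means of 6.25 to 25 days:

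| Per-patient SD | Power, 64 per arm | Power, 128 per arm |
|---|---|---|
| 100 | 0.050–0.051 | 0.050–0.051 |
| 10 | 0.054–0.108 | 0.057–0.169 |
| Poisson (2.5 to 5.0) | 0.108–0.289 | 0.169–0.513 |

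None reaches 0.80. Under Poisson variation d = 0.05√mean, so 64 per arm would need a mean of (0.499/0.05)² ≈ 100 days per patient per year.

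**The case against.** The strongest reply is that two claims of different certainty are involved. That 64 does not follow from 5%, 1250 and 100 is certain, but at face value this error is on the safe side, because 64 exceeds 42. The low power depends on how the SD is read, and the SDs of 10 and 3.54 and the CVs are not in the protocol. This stands as a limit on the individual power figures. It does not rescue the claim: the face-value reading is valid only if the difference and the SD are both on the scale of the randomised patient. Reading the SD as 100/100 = 1 day per patient gives the same power of 0.94, but an SD of 1 day lies well below the Poisson value for a mean of 12.5. It is not credible where, as section 4b says, "the patient population will be a mix with respect to socio-demographic and psychopathological parameters".

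A second reply is that 64 may be a total. The one-sided normal formula with d = 0.625 gives 31.7, so 32 per arm and 64 in all. That is a possible origin, so d = 0.50 should not be taken as the known source. It does not repair the text, which asks for 64 in each group.

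Third, the correction changes only wording, and section 12 expresses an expectation rather than a promise. That is true, but the statement concerned is the trial's only power claim for its primary outcome.

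**Conclusion.** The concern holds. It is certain that 64 per arm does not follow from the stated inputs, which at face value give 42 two-sided or 33 one-sided. It is also certain, without knowing the mean, that 80% power for a 5% reduction at 64 per arm needs a between-patient SD of about 10% of the mean. For the centre-wide mean of 12.5 days that is 1.25 days, 80 times smaller than the stated 100 if that figure is per patient.

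The power values are conditional. They rest on 12.5 days as the control mean, a two-sided 5% t-test, and the SD readings shown. On those terms, power is 5% to 17% per delivery model and 5% to 29% pooled. The most favourable case examined in varying the mean (25 days, Poisson SD, both models pooled) reaches 51%. The claim of 0.80 must be corrected.

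**What to change.** Keep the 256 patients. In section 7a:
- delete the claim of power 0.80 for a 5% reduction, and the closing sentence that rests on it;
- state the control mean, the absolute difference, the SD with its source, and the sidedness, all per patient over 12 months;
- state what the trial can detect with 80% power at two-sided 5%: about 0.50 SD per delivery model (64 against 64) and about 0.35 SD with A and B pooled (128 against 128). As an illustration only, an assumed SD of 10 days makes these 5.0 and 3.5 days.

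In section 12 (Subgroup analyses), withdraw the statement that the power calculation supports separate analyses of A and B, or qualify it with the 0.50 SD detectable difference. Making the pooled comparison primary is an option, but the correction does not require it.

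The cost is rewording in two sections and, if the records allow it, one query of the 2021 data for a per-patient SD. That SD would describe all centre patients and may not fit long waiters, which should be said alongside it. The detectable differences in SD units can be stated without the query. No extra patients are needed. The drawback is that the stated detectable effect becomes less favourable.

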## 2b Objectives

The objective of the current naturalistic/pragmatic randomized study is to test the feasibility and efficiency of the Thoughtful program in an unselected waiting list patient population from a psychiatric out-patient clinic in the University Hospital of North Norway.

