# Randomization

---

8a Sequence generation,

9 Allocation concealment mechanism

10 Implementation

During the trial period 64 waiting list patients per month in 4 months will be allocated.  
The patients are 1:1 computer randomized to trial/control group.

See also 11a.

---

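### Section 2b calls the waiting-list population unselected, but 7a fills the trial by longest wait: a modest limit on generalising, to be met by rewording 2b and adjusting the primary comparison for baseline

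*Protocol*

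**What the plan says.** Section 2b sets the objective "in an unselected waiting list patient population from a psychiatric out-patient clinic", with no qualifier on the word unselected. Section 4a opens eligibility widely: "All norwegian speaking patients on the outpatient clinic waiting list are considered eligible for the study". It explains the openness in clinical terms: "no patients will be a priori excluded from the study population for any clinical reason". Section 4b expects the patients to be mixed "with respect to length of waiting period & previous treatment measures".

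Section 7a then gives the rule for filling the trial: "Currently around 300 patients are on waiting list. Prioritizing long waiting time we enroll and randomize 256 patients in the trial". The Randomization section adds the pace: "64 waiting list patients per month in 4 months will be allocated". It does not say whether the long-wait priority is applied once to the list as it stands or again each month.

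Waiting time does not reappear after that. Section 8b states that randomisation is unrestricted, 12a names ANOVA without a covariate, and the subgroup section considers only the two delivery groups and the three services. The SAP was not available for this review.

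**The concern.** Length of wait is a patient characteristic, and filling places by it is a form of selection. A result reported for an unselected waiting list would cover the shortest waiters, whom the rule passes over.

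The characteristic may also bear on the primary outcome. Section 6a counts contact days over 12 months from intervention start, and section 5 lets every enrolled patient keep their place in the queue. How much of those 12 months falls after regular treatment begins plausibly depends on queue position. The protocol gives no data on this, so it is a reason for care and not an established effect.

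At stake are the population to which the conclusion applies and some precision. Waiting time and earlier contacts are baseline facts that 4b itself names as sources of variation, and the stated analysis makes no use of them.

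**Working it through.** **Inputs from the protocol.** List of about 300, 256 enrolled with priority to long waits, four groups of 64 (7a); 64 per month for 4 months (Randomization).

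**The plan's own total.** 4 groups × 64 = 256, and 4 months × 64 = 256. The two agree. Whether 64 per group follows from the stated SD and effect is a separate question and does not bear on this point.

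**Share of the list enrolled, no new referrals.** 256/300 = 85.3%. Left out: 300 − 256 = 44, and 44/300 = 14.7%.

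**Shift in waiting time.** Assume strict longest-first ordering, which gives the largest shift. The protocol gives no distribution of waits, so two shapes are assumed. With p = 256/N:

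- Normal waits: enrolled mean minus list mean = φ(z)/p in SD units, where z is the (1 − p) quantile. For N = 300, z = −1.05 and the shift is 0.27 SD.
- Exponential waits: enrolled mean / list mean = 1 − ln p. For N = 300 this is 1 − ln 0.853 = 1.16.

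New referrals enter behind everyone already waiting, so under strict ordering they enlarge the part of the pool not sampled. Inflow is not stated; the pools above 300 are assumptions that show the range.

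| Pool N | Enrolled 256/N | Left out | Normal shift (SD) | Exponential ratio |
|---|---|---|---|---|
| 300 (7a) | 85% | 44 | 0.27 | 1.16 |
| 350 (assumed) | 73% | 94 | 0.45 | 1.31 |
| 400 (assumed) | 64% | 144 | 0.58 | 1.45 |
| 500 (assumed) | 51% | 244 | 0.78 | 1.67 |

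**What this could do to the estimate.** Let k be the effect in those left out divided by the effect in those enrolled. Whole-list effect / trial effect = p + (1 − p)k. For N = 300:

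- k = 0: 0.853 + 0 = 0.85
- k = 1: 0.853 + 0.147 = 1.00
- k = 2: 0.853 + 0.293 = 1.15

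So even if the left-out patients gained nothing, or twice as much, the whole-list effect would lie within about 15% of the trial's.

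**What baseline adjustment would give.** Let R be the correlation between follow-up contact days and the two covariates taken together (prior-year contact days and waiting time). The share of residual variance removed is R². The protocol gives no value; the assumed range is 0.3 to 0.5.

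- R = 0.3: 0.3² = 9%. Equivalent unadjusted size per group: 64/0.91 = 70.
- R = 0.5: 0.5² = 25%. Equivalent unadjusted size per group: 64/0.75 = 85.

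**The case against.** The best defence is that 4a tells the reader what unselected means: nobody is kept out for diagnosis, co-morbidity, severity or treatment. Read that way, an ordering rule for filling 256 places does not contradict the objective, and 4b still expects mixed waiting times. Most of this stands, and it is why the correction to 2b is a matter of wording. What remains is that 2b uses the word without that limit, and a reader of the conclusions would not know that the shortest waiters were passed over.

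It is also fair to say that only the protocol is at hand, that covariates are often set in an SAP, and that an unadjusted randomised comparison is valid. The absence of covariates from 12a is therefore not an error. Adjustment is recommended because it is cheap and usually gains precision. If the correlation is near zero the gain vanishes, at the cost of two degrees of freedom.

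Three stronger readings are tempting and are not supported:

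- A reader might infer that the trial cannot answer for the population in its objective. With 85% of the list enrolled on the protocol's own figures, it largely can.
- A reader might infer that most of the eligible pool is missed, taking the centre's yearly patient count (14,621/12.5 ≈ 1,170, from 7a) as inflow. That count covers the ward and emergency team and would include continuing patients, so it is not a referral rate for this list.
- A reader might infer bias between arms. The priority acts before allocation and equally on both arms, so it causes none.

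**Conclusion.** The point holds as a modest limit on generalising plus an opportunity for precision. Sections 2b and 7a do not describe quite the same population: the sample is clinically unselected but weighted to longer waiters. On a static list of 300 about 85% are enrolled, the mean wait is shifted by about 0.27 SD (normal) or a factor of 1.16 (exponential), and the whole-list effect would be 0.85 to 1.15 times the trial's if the left-out effect were 0 to 2 times that of the enrolled. These figures assume strict ordering and no inflow. With inflow the share falls and the shift grows, by an amount the protocol does not let anyone calculate. The randomised comparison is unaffected. The 9% to 25% reduction in residual variance rests wholly on the assumed correlation.

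**What to change.** 1. **Population.** In 2b and in the conclusions, describe the population as clinically unselected waiting-list patients with priority to long waiters. In 7a, state whether the priority is applied once to the list or again each month. Report waiting time for enrolled and non-enrolled patients, so that readers can see the shift. Cost: two sentences and a summary of waiting times from the record system. The enrolment rule itself can stay, and the trial title does not say unselected and needs no change.

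2. **Analysis.** In 12a, replace plain ANOVA of contact days with a baseline-adjusted comparison, for example ANCOVA. Pre-specify as covariates the contact days in the 12 months before randomisation and the waiting time at randomisation. Both should be obtainable from DIPS, the system that the Data protection section names for administrative data. Cost: one slightly larger extract and one sentence. If the SAP already sets these covariates, 12a need only refer to it.
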